3.6.2 Follow-up

A member of the study team will perform reviews of the subject's electronic health record at regular intervals. Subjects will be contacted via telephone to assess whether they have been hospitalized or sustained any other adverse cardiovascular events. MACE will be defined as (1) acute coronary syndrome, (2) hospitalization for HF, (3) serious cardiac arrhythmia, (4) PAD, (5) cerebrovascular events, and (6) CV death.^{74,101-106} Event ascertainment will be an iterative process implemented every six months that will begin with querying each participant about the interval occurrence of any of the outcome events or any hospitalizations. Positive indications from study participants about a hospitalization or possible event will be followed by collection of selected medical records from the inpatient setting. Records will include administrative hospital codes and copies of relevant portions of the medical record, including admission and discharge notes, progress notes, laboratory studies, ECGs, radiographic studies, and any other diagnostic testing or procedure notes. Individual events will be defined as described in **Table 2**:

Table 2. Summary of adjudicated outcome events	
Outcome Event	Summary of Definitions
Acute Coronary Syndrome	New universal definition of MI by the American Heart Association. ¹⁰⁷ Acute MI types 1-3: Acute myocardial injury with clinical evidence of acute myocardial ischemia and with detection of a rise and/or fall of cardiac troponin (cTn) values with at least 1 value above the 99th percentile upper reference limit (URL) and at least 1 of the following:

CONFIDENTIAL

	
 • Symptoms of myocardial ischemia • New ischemic ECG changes • Development of pathological Q waves • Imaging evidence of new loss of viable myocardium or new regional wall motion abnormality in a pattern consistent with an ischemic etiology • Identification of a coronary thrombus by angiography or autopsy (not for types 2 or 3 MIs). 
Percutaneous coronary intervention (PCI)-related MI (type 4a MI) and Coronary artery bypass grafting (CABG)-related MI (type 5 MI):
 
 • Coronary procedure-related MI ≤48 hours post-procedure, cTn >5-fold (type 4a MI) or >10-fold increase (type 5 MI) of the 99th percentile URL in patients with normal baseline values. Patients with elevated preprocedural cTn values must manifest a change from the baseline value of >20%. • In addition, at least 1 of the following: 
 - New ischemic ECG changes (this criterion is related to type 4a MI only) - Development of new pathological Q waves - Imaging evidence of loss of viable myocardium that is presumed to be new - Angiographic findings consistent with a procedural flow-limiting complication such as coronary dissection, occlusion of a major epicardial artery or graft, or disruption of collateral flow - Isolated development of new pathological Q waves if cTn values are elevated and rising 
Types 4b (MI stent thrombosis) and type 4c MI (restenosis): must meet type 1 MI criteria.

Coronary Revascularization	Percutaneous angioplasty or stent placement for obstructive coronary artery disease or CABG
Hospitalization for HF	Hospitalization for clinical symptoms of HF in the setting of objective confirmatory evidence including radiographs, evidence of pulmonary congestion/edema, physical examination, invasive hemodynamic monitoring, or echocardiographic confirmation. Admission must include administration of intravenous diuretics, escalation of diuretic doses and/or use of inotropes, volume removal by ultrafiltration or renal replacement therapy for decongestion, or mechanical circulatory support. Relevant echocardiographic information will be reviewed to determine if the event is consistent with HF with reduced ejection fraction (EF <40%), mid-range EF (40-49%), or preserved EF (≥50%). ¹⁰⁸
Incident Serious Cardiac Arrhythmia	Categorized as follows: 
 • Resuscitated cardiac arrest • Ventricular fibrillation • Sustained ventricular tachycardia • Selected instances of non-sustained ventricular tachycardia • Initial episode of atrial fibrillation or flutter, severe bradycardia or heart block • Postoperative tachyarrhythmias following CABG or other cardiac surgery
Peripheral arterial disease	One of the following must be present: 
 • PAD with resultant amputation • Surgical or percutaneous revascularization procedures such as angioplasty and artery-artery bypass graft
Cerebrovascular Events	Categorized as follows: 
 • Intraparenchymal hemorrhage • Subarachnoid hemorrhage • Large-vessel cerebral infarction • Cardioembolic cerebral infarction • Small-vessel cerebral infarction • Cerebral infarction not otherwise specified • Transient ischemic attack: Acute disturbance of focal neurological or monocular function with symptoms lasting less than 24 hours and thought to be due to arterial thrombotic or embolic vascular disease

CONFIDENTIAL

Death Events	
Cardiovascular death:
 
• Atherosclerotic coronary heart disease death• Cerebrovascular death• Other atherosclerotic disease death (non-coronary/non-stroke)• Sudden cardiac death• Other CVD death (including death from HF) 
Other Death

--------------	---

3.7 Unscheduled Visits

We anticipate no unscheduled visits. We anticipate that the only situation in which this would occur is if a study subject requests a meeting with the investigator to discuss any issues related to the study.

3.8 Subject Withdrawal

Subjects may withdraw from the study at any time without impact to their care. The Investigator may also withdraw subjects who violate the study plan, to protect the subject for reasons related to safety, or for administrative reasons. It will be documented whether or not each subject completes the study.

4 Statistical Plan

4.1 Data analysis plan

To characterize cardiac and extracardiac phenotypes in COVID-19 survivors, we will use latent class analysis with finite mixture modeling to classify individuals into mutually exclusive and exhaustive subgroups, maximizing within-group similarities and between-group differences on the basis of baseline covariates ¹⁰⁹⁻¹¹². Latent class models will be compared across successive numbers of subgroups and the optimal number of groups will be determined using the parametric bootstrap likelihood ratio test, Akaike's Information Criterion, Bayesian Information Criterion, and sample-size adjusted BIC ^{113,114}. We will use other clustering methods for corroboration of our identified phenotypes, including Gaussian mixture models via the expectation–maximization algorithm ⁷⁹, and consensus clustering ¹¹⁵ to evaluate the stability of the discovered clusters. Descriptive statistics will compare patients across phenotypes using Student's t-test, Wilcoxon rank sum, or Chi-square test, as appropriate. We will then assess for differences in quality of life and functional status across phenotypes using multinomial logistic regression. We will separately analyze the trajectory of each of the quantitative measures of vascular health and kidney function using mixed effects growth curve models.¹¹⁶ Where necessary, we will supplement these analyses with marginal models estimated by generalized estimating equations.¹¹⁷ We will assess for varying length of follow-up among subgroups to evaluate for any potential bias this may introduce. We will assess for effect modification by sex and race due to potentially important differences in COVID-19 outcomes¹¹⁸⁻¹²⁰ and trajectory of vascular and kidney health.^{121,122} We will also use methods that classify participants according to their vascular and kidney health trajectories, using each individual parameter and extended to multiple parameters. We will use the latent class mixed effects model^{123,124} to analyze trajectories of vascular and kidney health within our study population. The latent class mixed effects model introduces an additional variable to represent class membership, which can be modeled through a multinomial logistic regression.

The endpoint of MACE will be evaluated as a time-to-event endpoint from the date of discharge from the index hospitalization for COVID-19 and from the date of the first study visit, accordingly. We will examine the associations of severity of hospitalization, baseline covariates, and post-discharge cardiac and extra-cardiac phenotypes with this failure-time event using Kaplan-Meier curves and Cox proportional hazards regression ¹²⁵. We will use the multivariable Cox model to

CONFIDENTIAL

estimate the effects of the primary exposure adjusting for baseline covariates. We will use time by covariate interaction terms and examine residual plots to assess the adequacy of model fit ¹²⁶. If the proportional hazards assumption is violated, a time by predictor interaction term will be added to the model to allow for changes in the HR over time. Secondary analyses will evaluate death prior to the event as a competing risk, including incorporation of the composite outcome with the cumulative incidence function ^{127,128}. We will assess for effect modification by sex and race due to sex- and race-related differences in COVID-19 outcomes ¹¹⁸⁻¹²⁰ and risk of MACE ^{121,129}.

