Statistical Methodology	Statistical techniques will include t-tests, linear regression models, mixed models, network analysis, pathway analysis, and machine-learning approaches. The relationship between phenotypic profiles and incident risk will be assessed using a combination of Cox regression, Poisson regression, and Kaplan-Meier survival analyses, as needed. Corrections for multiple comparisons will be performed with false discovery rate correction, Bonferroni correction, or principal-components analysis-based correction, as appropriate.
Data and Safety Monitoring Plan	The Investigators will be responsible for the data quality management and the ongoing safety of subjects.

CONFIDENTIAL

[figure not shown]
Background and Study Rationale

1 Introduction

A1. With the ongoing spread of coronavirus disease 2019 (COVID-19), there is a growing population of COVID-19 survivors. COVID-19 is a public health crisis. Severe acute respiratory syndrome coronavirus 2 (SARS-CoV-2), the virus responsible for the COVID-19 pandemic, is associated with a high risk of pneumonia and multiorgan dysfunction.¹⁻⁴ Despite containment and mitigation efforts, COVID-19 continues to spread. As the case fatality rate for COVID-19 is estimated at <1%,⁵ it follows that along with the pandemic increase of COVID-19 cases, there will be a marked increase of COVID-19 survivors in the general population.

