4.2 Power calculations

We will enroll 200 COVID-19 survivors following recovery from their hospitalization and 80 controls. For analyses of trajectory of vascular and kidney health, accounting for multiplicity across multiple outcome parameters at an alpha at 0.0025, ¹³⁰ we will have >80% power to observe, for example, a mean difference in slope of PWV of 0.8 m/s and eGFR of 4 mL/min/1.73m² per 18-month visit interval across COVID-19 survivors and non-COVID-19 controls, assuming intraclass correlation coefficient of 0.1 and 20% loss to follow-up.¹³¹ For determining the association of hospitalization severity with risk of MACE, the most conservative endpoint in the study, we assumed a cumulative event rate of 5% over 5 years of follow-up ^{6,7}, accounting for our exclusion of individuals with prior CVD. Assuming a retention rate of 80%, we will have 90% power at an alpha of 0.05 to detect a regression coefficient of 0.9 in the Cox model ^{132,133}. In analyses evaluating for sub-phenotypes and risk factors for MACE, using a conservative Bonferroni approach to account for multiplicity across several risk factors ¹³⁰, we will have over 90% power at an alpha of 0.005 to detect a regression coefficient of 0.9 for every standard deviation difference in parameter. Power calculations were performed using PASS16 ¹³⁴.

5 Study Administration, Data Handling, and Record Keeping

All information obtained as part of protocol will be maintained in locked research files. Electronic data will be stored in a password secured database (REDCap). This database will be available only with secure high-level password protection to safeguard the privacy of the participants. Any source documents for each patient involved in the protocol, other than the patient's electronic medical chart, will be maintained in a centralized, secured location.

Data collected will contain protected health information (PHI) including name, date of birth, and medical record number. Information about study subjects will be kept confidential and managed according to the requirements of the Health Insurance Portability and Accountability Act of 1996 (HIPAA). Research data will be stored in a centralized, secure location (locked cabinets in the PI's research space).

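### Section 4.1 allows significance tests across latent classes on the same baseline variables that formed the classes; those p-values are circular

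*Combined protocol and SAP*

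**What the plan says.** Section 4.1 (Data analysis plan) uses latent class analysis with finite mixture modelling to sort survivors into subgroups, "maximizing within-group similarities and between-group differences on the basis of baseline covariates". The number of classes is chosen by several criteria: "the optimal number of groups will be determined using the parametric bootstrap likelihood ratio test", together with AIC, BIC and sample-size adjusted BIC. Gaussian mixture models and consensus clustering are added for corroboration and "to evaluate the stability of the discovered clusters".

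The comparison step follows: "Descriptive statistics will compare patients across phenotypes", by t-test, rank-sum or chi-square test as the data require. The section does not say which variables are compared, sets no alpha for the step, and does not list the covariates that enter the class model.

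A separate step covers outcomes: "We will then assess for differences in quality of life and functional status across phenotypes using multinomial logistic regression". MACE is related to phenotypes by Kaplan-Meier and Cox methods later in the same section. The synopsis (Statistical Methodology) adds a general statement: "Corrections for multiple comparisons will be performed with false discovery rate correction, Bonferroni correction, or principal-components analysis-based correction, as appropriate".

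**The concern.** A two-sample test assumes that group membership was fixed without looking at the variable being tested. Here membership is computed from the baseline covariates by a method that seeks separation on them. If one of those covariates is then compared across the classes, its group means differ because of how the groups were made, even when all participants come from one homogeneous population. The nominal 5% error rate no longer applies.

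The false discovery rate, Bonferroni and principal-components corrections in the synopsis deal with the number of tests. They do not deal with using the same data to define the groups and then to test them, so they do not repair these p-values.

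At stake is a table of class characteristics in which some p-values carry no information and a reader cannot tell which. There is also a boundary to settle. KCCQ, EQ-5D-5L, PROMIS, the 6-minute walk and SPPB are all collected at the baseline visit (Sections 3.1 and 3.6.1), and Section 4.1 does not define which baseline covariates form the classes. Nothing written keeps these measures out of the model.

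**Working it through.** The documents give no figure for this step, so there is nothing to reproduce. The check has three parts.

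**1. The mechanism in its simplest form.** Take n = 200 from Section 4.2 ("We will enroll 200 COVID-19 survivors following recovery from their hospitalization and 80 controls"), one standard normal variable, one population, split at its median into two groups of 100.
- Group means: ±√(2/π) = ±0.798, so the difference is 1.596.
- Within-group SD: √(1 − 2/π) = 0.603.
- Standard error: 0.603 × √(1/100 + 1/100) = 0.0853.
- t ≈ 1.596 / 0.0853 ≈ 18.7, although there is only one population.

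In 500 simulated splits of this kind, every t-test gave p<0.05. With several variables the separation is shared among them, so the effect on each is smaller.

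**2. Simulation with a mixture model.** From the documents: 200 survivors, and the t-test and Wilcoxon test. Assumed, because the documents do not say: 5 or 10 continuous class-forming variables; pairwise correlation 0, 0.1 or 0.3, or independent lognormal (skewed) variables; two-sided alpha 0.05. The data contain no classes. The fitted model is a normal mixture with local independence and equal variances. The criteria choose among one to three classes; the tests use modal assignment to two imposed classes. There were 150 runs per setting, and runs with a class of fewer than 3 people were dropped from the test results.

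| Variables | t-test p<0.05, class-forming | Wilcoxon p<0.05, class-forming | t-test p<0.05, independent variable left out | More than one class kept: BIC / adjusted BIC / AIC |
|---|---|---|---|---|
| 5, independent | 59.5% | 59.3% | 2.0% | 0% / 27% / 37% |
| 5, correlation 0.1 | 90.0% | 89.9% | 8.7% | 15% / 96% / 96% |
| 5, correlation 0.3 | 100% | 100% | 4.0% | 100% / 100% / 100% |
| 5, skewed | 29.7% | 29.9% | 7.5% | 100% / 100% / 100% |
| 10, independent | 52.2% | 51.5% | 6.7% | 0% / 28% / 46% |
| 10, correlation 0.1 | 92.4% | 92.3% | 2.7% | 72% / 100% / 100% |
| 10, correlation 0.3 | 100% | 100% | 6.0% | 100% / 100% / 100% |
| 10, skewed | 22.3% | 21.1% | 6.1% | 97% / 100% / 100% |

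At least one class-forming variable reached p<0.05 by t-test in every analysed run of every setting. The benchmark for valid independent tests is 1 − 0.95^5 = 22.6% for five and 1 − 0.95^10 = 40.1% for ten. The eight left-out rates average 0.437 / 8 = 5.5%; with 150 runs the standard error of a true 5% rate is √(0.05 × 0.95 / 150) = 1.8 percentage points.

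A second simulation (200 data sets per setting; k-means, which the plan does not name, and a diagonal Gaussian mixture; two classes imposed) agrees. For independent variables the rates were 78% and 65% with 5 variables, 68% and 56% with 10, and 57% and 47% with 20. All were 100% at correlation 0.3. The left-out variable stayed at 4.5% to 5.5%.

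**3. Does class selection prevent the comparison?** With independent normal variables BIC kept one class in every run, so no comparison would follow. A small run of the bootstrap likelihood ratio test (40 data sets, 39 bootstrap samples, 10 variables) kept two classes over one in 10% of independent data sets and in 100% at correlation 0.1. When it did, 55% and 96% of class-forming variables had p<0.05. At correlation 0.3 or with skewed variables, BIC, adjusted BIC and AIC kept more than one class in 97% to 100% of runs.

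Correlated measures are plausible here. Section 3.6.1 computes perfused vessel density as vessel density times the proportion perfused, and uses the carotid tonometry waveform for both local carotid pulse wave velocity and central pulse pressure.

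**The case against.** The plan labels the step descriptive and names no variables, so the tests may be meant for variables outside the class model, where they are sound. The number of classes and their stability are judged beforehand by other tools. Quality of life, functional status and MACE have their own analyses. The simulations impose two classes, rest on inputs the documents do not give, and reach 100% only where the fitted model's local-independence assumption is broken.

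Much of this stands, and it limits the point. A reader might infer that the comparisons will be significant even when no phenotypes exist. The documents do not support that: if selection keeps one class there is nothing to compare, and among class-forming variables the share significant ranged from about a fifth to all. A reader might also infer that these p-values are the plan's evidence that phenotypes are real, and so that the primary objective rests on them. Section 4.1 says no such thing; it uses information criteria, the bootstrap test and consensus clustering for that purpose.

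What does not stand is the defence that the descriptive label or the selection step removes the problem. The sentence names three hypothesis tests and exempts no variable, and selection was not a dependable guard once variables were correlated or skewed.

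**Conclusion.** The point holds in a limited form. Followed as written, Section 4.1 permits circular p-values for any variable that helped form the classes. With no true classes and two classes imposed, 22% to 100% of t-tests on such variables reached p<0.05 (21% to 100% by Wilcoxon), against about 5% for an independent left-out variable. The size depends on the assumed number, correlation and shape of the variables, but every setting tried was well above 5%.

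Two conditions bound it: the variable must be in the class model, and more than one class must be retained. The outcome analyses are not circular unless their measures enter the model, which the plan should rule out in writing. This is a defect in how one step is specified; it does not invalidate the study's objectives.

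**What to change.** Amend Section 4.1 as follows.

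- List in advance the variables that enter the class model, and state that KCCQ, EQ-5D-5L, PROMIS, the 6-minute walk and SPPB are kept out of it.
- Report class-forming variables by class as means or percentages with standardised differences, without p-values.
- Confine hypothesis tests to variables outside the model, using methods that suit the number of classes retained (for example ANOVA, Kruskal-Wallis or chi-square).
- State that the one-class model is a candidate and which selection criterion decides if the criteria disagree.
- Add that a significant result on a held-out variable shows association with class, not that discrete classes exist. The near-5% rate above is for a variable independent of the class model; a held-out measure correlated with the class-forming variables could differ across classes cut from a continuum.

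The cost is SAP wording only. No new data are needed and no valid analysis is lost.

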- (1) To characterize cardiac and extracardiac phenotypes in COVID-19 survivors, and their relationship with: (a) quality of life; (b) functional status; (c) aerobic capacity; (d) prognosis.
- (2) To determine if the severity of COVID-19 is associated with measures of organ-specific structure and function after recovery.
- (3) To perform prospective follow-up of the cohort for the development of death, heart failure-related hospitalizations, and other adverse cardiovascular outcomes.
- (4) To establish a biorepository for future discovery.

3 Investigational Plan

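### The planned multinomial regression would report odds of phenotype membership, not the promised difference in quality of life and function, and the plan does not say how classification error is handled.

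*Combined protocol and SAP*

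**What the plan says.** Objective 1 in section 2 is: "To characterize cardiac and extracardiac phenotypes in COVID-19 survivors, and their relationship with: (a) quality of life; (b) functional status". Aerobic capacity and prognosis follow as (c) and (d).

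Section 4.1 (Data analysis plan) sets out the route. Latent class analysis with finite mixture modelling will "classify individuals into mutually exclusive and exhaustive subgroups", and this is done "on the basis of baseline covariates". Those covariates are not listed. Then: "Descriptive statistics will compare patients across phenotypes using Student's t-test, Wilcoxon rank sum, or Chi-square test, as appropriate". The variables to be compared are not named. The next sentence is the one at issue: "We will then assess for differences in quality of life and functional status across phenotypes using multinomial logistic regression".

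The plan does not state:
- the dependent variable of that multinomial model;
- the rule for assigning people to classes (modal, probability-weighted or one-step);
- whether quality-of-life or functional measures are among the class-forming covariates;
- any adjustment set for this comparison;
- any handling of classification uncertainty.

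The measures themselves are described in sections 3.1 and 3.6.1: KCCQ, EQ-5D-5L and PROMIS questionnaires, distance covered in the 6-minute walk test, and the SPPB, scored 0 to 12.

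**The concern.** The sentence promises differences in quality of life and function between phenotypes. A reader of the results will want to know how many KCCQ points or metres of walking separate one phenotype from another, after adjustment. A model with phenotype on the left-hand side does not give that. It gives the change in log-odds of belonging to a class, relative to a reference class, per unit of score. That quantity depends on the spread of the score as well as on the difference.

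The second issue concerns the order of the steps. Classes are estimated, people are placed in them, and the groups are then compared. If the placement is treated as known, people put in the wrong class blur the comparison, and the intervals leave out the uncertainty about class. With 200 survivors (section 4.2), a loss of that kind could matter for Objective 1(a) and (b).

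**Working it through.** The plan gives no effect size, SD, number of classes, entropy, alpha or power for this comparison, so there is no stated figure to reproduce. The check has three parts. The first uses the text alone; the other two use assumptions, which are named.

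**1. Which variable is the outcome?** Multinomial logistic regression needs a nominal dependent variable. The sentence involves quality of life, functional status and phenotype. The first two are measured as scores or distances and are not cut into categories anywhere in the plan. Phenotype is the only nominal variable. Later in section 4.1, the latent class mixed model for trajectories introduces "an additional variable to represent class membership, which can be modeled through a multinomial logistic regression", which again puts class on the outcome side. Class as outcome is thus the natural reading, but it is an inference. The alternative, cutting the scores into unordered categories, is not described and would discard their order.

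**2. What would the coefficient mean?** For two normal groups with equal variance and mean difference δ, the logistic coefficient of class on score is β = δ / SD². Take δ = 5 points (assumed):

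| Assumed SD | β = 5 / SD² (absolute value) |
|---|---|
| 8 | 5/64 = 0.078 |
| 10 | 5/100 = 0.050 |
| 15 | 5/225 = 0.022 |
| 20 | 5/400 = 0.0125 |

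The same 5-point difference produces coefficients that vary about sixfold (0.078 / 0.0125 = 6.2). The model can test whether score and class are associated, but it does not report the difference.

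**3. How much could classification error matter?** Assume two equal classes, modal assignment, and error unrelated to the score given true class. With class separation D in SD units, the misclassification rate is p = Φ(−D/2). The observed difference in means is the true one times (1 − 2p), so the shrinkage is 2p:

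| D (assumed) | p | Shrinkage 2p |
|---|---|---|
| 4.0 | 2.3% | 5% |
| 3.5 | 4.0% | 8% |
| 3.0 | 6.7% | 13% |
| 2.5 | 10.6% | 21% |
| 2.0 | 15.9% | 32% |
| 1.5 | 22.7% | 45% |

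A simulation checked this with the class model actually fitted: N = 200, two equal classes, six Gaussian indicators, modal assignment, true difference −5 points, SD 10, about 400 runs per row. The uncorrected column is a mean over runs and the corrected column a median. The correction is a three-step estimate of BCH type. The last column is the logistic coefficient with assigned class as outcome, divided by the coefficient with true class as outcome.

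| Mean entropy | Uncorrected difference | Corrected difference | Coefficient ratio |
|---|---|---|---|
| 0.85 | −4.47 | −4.85 | 0.89 |
| 0.65 | −3.81 | −4.57 | 0.75 |
| 0.54 | −3.34 | −4.62 | 0.63 |
| 0.49 | −2.34 | −3.57 | 0.46 |

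The class-as-outcome coefficient is therefore attenuated much as the mean difference is. The correction recovers most of the loss when classes are reasonably separated, and less when separation is poor.

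**The case against.** Several points on the other side have force.

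- **A reader might infer that the plan takes the assigned class as a known outcome.** It does not say this. Neither the dependent variable nor modal assignment is written, and a one-step latent class regression is not excluded. If a one-step model is intended, the misclassification issue falls away. This stands, and it limits that part of the point to a gap in specification.
- **A reader might infer that the analysis is invalid or misses the objective.** It does not. Objective 1 speaks of a relationship, and a regression with class as outcome tests one. What changes is the estimand and its scale. The mismatch is with the analysis sentence, which promises differences.
- **Score differences may be available elsewhere.** The t-tests and Wilcoxon tests could supply them, and the synopsis says: "Statistical techniques will include t-tests, linear regression models, mixed models, network analysis, pathway analysis, and machine-learning approaches". This stands only in part. The tests are labelled descriptive, name no variables and are unadjusted, and linear regression is not tied to these outcomes. An adjusted difference is still not planned.
- **A reader might infer that the result is biased toward no difference by 21% to 45%.** The documents support neither the direction nor the size. If quality-of-life or functional measures are among the unlisted class-forming covariates, circularity could push the difference upward. The percentages assume two equal classes and a separation the plan does not give. The 45% case is also one that the plan's own selection step might not reach. In a simulation at D = 1.5 and N = 200, BIC chose two classes in 14% of runs with six indicators and 1% with twelve. AIC, also listed, usually did choose two, so the case remains possible.

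**Conclusion.** The point holds in two parts of unequal strength.

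The firmer part concerns the model. On the natural reading, the named method reports odds of class membership per score point, and no planned analysis reports the adjusted difference in score between phenotypes. This rests on the measures being scores or distances that are not categorised, which the documents bear out. It does not invalidate the test of association.

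The conditional part concerns classification error, for which no handling is stated. If the scores do not help to form the classes and classes are assigned and then treated as known, differences are probably attenuated. For two equal classes the loss runs from about 5% at a separation of 4 SD, through 21% at 2.5 SD, to 45% at 1.5 SD. These figures are illustrations. The true size cannot be found from the documents, and the direction could reverse if the scores are class indicators.

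**What to change.** In section 4.1, replace the multinomial sentence with the following specification:

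1. Each quality-of-life and functional score is the dependent variable in a linear or ordinal model, with phenotype as the predictor. Covariates are prespecified and are not themselves class indicators. Adjusted differences are reported with 95% intervals.
2. The class-forming variables are listed, and quality-of-life and functional measures are kept out of them.
3. Classification uncertainty is carried into the comparison by a one-step model or a bias-adjusted three-step method (BCH or maximum likelihood), at least as a sensitivity analysis. Entropy is reported so that readers can judge class separation.

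The cost is a few lines of SAP text and modest programming; no new data are needed. Intervals will be somewhat wider because class uncertainty is counted. If classes turn out poorly separated, the correction will be incomplete at this sample size: in the simulation it reached −3.57 against a true −5 at the lowest entropy. That is a further reason to report entropy alongside the estimates.
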